1.2 SCHEMA

Figure 1 - Graphical study design

AE: adverse event; ORR: objective response rate; RECIST: Response Evaluation Criteria in Solid Tumors

1.3 SCHEDULE OF ACTIVITIES (SOA)

Evaluation ^a	Screening	Treatment Period ^b				End of Treatment	Observation Period ^c			Survival Phone Call Follow-up ^d	Notes
		Cycle 1		Cycle 2 and beyond ^e			EOT Visit	Follow-Up	Follow-Up	Follow-Up	
		Visit 1	Visit 2	Visit 3+				Phone Call FU			
Cycle Day (Visit window in Days)	D-28 to D-1	D1	D8 ^f (±1)	D15 ^f (±1)	D1 (±3)	30 days (+/- 7 days) after last IMP or at initiation of further therapy	3 months after last IMP admin ±7 days	6 months after last IMP admin ±7 days	Every 3 months after FU visit 2 ± 7 days	Every 3 months +/- 14 days	
Informed consent	X										
Inclusion and exclusion criteria	X										
IRT contact	X	X			X	X					
Demography, medical/surgical and disease history	X										See Section 8
Body Weight / Height ^g	X	X	X	X	X	X	X				
Full physical examination	X					X					See Section 8.2.1
Directed Physical examination		X	X	X	X		X				See Section 8.2.1
Vital Signs	X	X	X	X	X	X	X				See Section 8.2.2
Performance status (ECOG)	X	X	X	X	X	X	X				
SpO ₂	X	As clinically indicated									

Evaluation ^a	Screening	Treatment Period ^b				End of Treatment	Observation Period ^c			Survival Phone Call Follow-up ^d	Notes
		Cycle 1			Cycle 2 and beyond ^e		Follow-Up	Follow-Up	Follow-Up		
		Visit 1	Visit 2	Visit 3+			Phone Call FU				
Cycle Day (Visit window in Days)	D-28 to D-1	D1	D8 ^f (±1)	D15 ^f (±1)	D1 (±3)	30 days (+/- 7 days) after last IMP or at initiation of further therapy	3 months after last IMP admin ±7 days	6 months after last IMP admin ±7 days	Every 3 months after FU visit 2 ± 7 days	Every 3 months +/- 14 days	
Laboratory and other investigations											
12-Lead ECG	X	X	As clinically indicated								See Section 8.2.3
LVEF	X	As clinically indicated									See Section 8.2.3
Troponin	X	As clinically indicated		X (Cycle 4 Day 1)	As clinically indicated						See Section 8.2.3 and Section 10.2
Pregnancy test	X	X			X	X	X	X			See Section 8.2.5 and Section 10.2
Hepatitis serology, CD4 counts and viral load	X ^h	As clinically indicated									See Section 10.2 and Section 10.7
Hematology	X	X	X	X	X	X	X				See Section 10.2
Coagulation	X	As clinically indicated									See Section 10.2
Blood Chemistry	X	X	X	X	X	X	X				See Section 10.2

[figure not shown]
Evaluation ^a	Screening	Treatment Period ^b				End of Treatment	Observation Period ^c			Survival Phone Call Follow-up ^d	Notes	
		Cycle 1			Cycle 2 and beyond ^e	EOT Visit	Follow-Up	Follow-Up	Follow-Up	Phone Call FU		
							Visit 1	Visit 2	Visit 3+			
Cycle Day (Visit window in Days)	D-28 to D-1	D1	D8 ^f (±1)	D15 ^f (±1)	D1 (±3)	30 days (+/- 7 days) after last IMP or at initiation of further therapy	3 months after last IMP admin ±7 days	6 months after last IMP admin ±7 days	Every 3 months after FU visit 2 ± 7 days	Every 3 months +/- 14 days		
Urinalysis ^g	X	X			X	X	X				See Section 10.2	
IMP												
SAR444245		X			X							
Hospitalization ^h		X										
AE/SAE assessment ^k	X	Continuously throughout treatment period					X				See Section 8.3	
Prior/Concomitant Meds	X	Continuously throughout treatment period									See Section 6.8	
First subsequent anti-cancer therapy						X	X	X	X	X		
Survival status										X		
Pharmacokinetic (PK) / Pharmacodynamic (PDy) / Immunogenicity assessments												
PK SAR444245	See PK flowcharts in Section 1.5.1 and Section 1.5.2											
ADA SAR444245	See PK flowcharts in Section 1.5.1 and Section 1.5.2											
PDy - Blood and tumor tissue collection ^{l,m}	See Biomarker Flowchart in Section 1.4											
Tumor assessment												
Brain imaging ⁿ	X										See Section 8.1	
CT/MRI ^o	X				X	X	X	X	X		See Section 8.1	

- a Evaluation: Screening assessments to be performed prior to first IMP administration unless otherwise indicated. There is no need to perform Cycle 1 Day 1 laboratory assessments that have been performed as part of screening within 3 days prior to first IMP administration. During the study treatment period, all assessments must be performed, and results should be reviewed by the investigator prior to IMP administration at that visit. After Cycle 1, samples for laboratory assessments (excluding PK & biomarker) can be collected up to 3 days prior to IMP administration. ICF must be signed before any study-specific procedures are performed and can be signed more than 28 days prior to first IMP administration. Screening time indicates the maximum time frame relative to the first IMP administration in which study procedures used to support eligibility are done.
- b Cycle: a treatment cycle is 21 days. See details in [Section 6.1](#) for IMP administration. If treatment cycles are adjusted, all procedures except tumor assessment imaging will be completed according to the cycle number. Tumor assessment imaging will be performed at fixed time points from C1D1 regardless of any treatment delays.
- c Observation Period: Participants who enter the Observation period will be followed differently depending on the reason leading to permanent IMP discontinuation. See [Section 4.1](#). For participant's convenience, all Follow-up assessments may occur during the same visit as that when tumor assessment is performed.
- d Survival Phone Call Follow-Up Period: Once the participant stops the tumor assessments due to PD or starts a new antineoplastic therapy, the participant moves into the Survival Follow-up Period and should be contacted by telephone approximately every 3 months \pm 14 days to assess for survival status. Updated survival status may be requested by the Sponsor at any time during the study.
- e For Cycle 4 visits, please refer to PK flowchart in [Section 1.5](#).
- f C1D8 and/or C1D15 visits must be performed on site for the following participants only: 1) Participants scheduled to have blood draws for biomarker assessment and/or ADA on Day 8; 2) Participants who will receive IMP on Day 8 and Day 15. For all other participants, these 2 on-site visits may be done remotely as appropriate based on investigator's discretion per institutional standard and local regulations. If this is the case, this must be documented in the source document. Sponsor may decide to cancel safety assessment on C1D8 and C1D15 if safety data justifies it.
- g Weight/Height: Height is required at baseline only. Weight is required at Screening and prior to starting each infusion. The total dose will be calculated based on the weight on the day of the infusion or the most recent weight assuming it was assessed in a reasonable time frame according to Investigator assessment. Study sites should make every effort to measure body weight as close to the infusion day as possible considering the variability of local process from site to site. If the infusion is prepared with the most recent weight assessed in a reasonable time frame, this will not prevent to assess the weight on D1 of each cycle.
- h For participants with known HIV, hepatitis B and hepatitis C infection under antiviral treatment to confirm controlled infection, and for all participants in Germany and Italy (see details and specific instructions in [Section 10.2](#) and [Section 10.7](#)).

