4 STUDY DESIGN

4.1 OVERALL DESIGN

This is a Phase 2, multi-cohort, un-controlled, non-randomized, open-label, multi-center study assessing the antitumor activity and safety of SAR444245 combined with other anticancer therapies in participants with advanced or metastatic gastrointestinal cancer.

This study is developed as a master protocol in order to accelerate the investigation of SAR444245 with various anticancer therapies by identifying early efficacy signals. This design is with the flexibility to open new treatment cohorts as new treatment combinations become available and close existing treatment arms that demonstrate minimal clinical activity or unacceptable toxicity.

The information that is introductory and common to all cohorts is included in the present document (“Master Protocol”), and cohort-specific elements are included in separate substudies. This study is designed with the flexibility to open new treatment arms or add new indications as permitted by scientific rationale.

A graphical presentation of the study schema is shown in the individual substudy.

Interactive Response Technology (IRT) will be used to control recruitment, assignment per site and to facilitate the handling, management, and accountability of drug supply.

The duration of the study for a participant will include:

- **Screening Period:** up to 28 days
- **Treatment Period:** enrolled participants will receive continuous treatment until progressive disease (PD), unacceptable adverse event (AE) or other full permanent discontinuation criteria as described in [Section 7](#); or completion of Cycle 35 (if applicable).
- **End of Treatment and Follow-up:** End of Treatment Visit will occur 30 days \pm 7 days from last IMP administration or prior to initiation of further therapy, whichever comes first. Participants will then enter the **Observation Period** and will be followed differently depending on the reason leading to **End of Treatment (EOT)**.
 1. Participants who discontinue study treatment **without PD** or who **complete 35 cycles of treatment without PD** will be followed every 3 months \pm 7 days from last IMP administration, for safety (as per Schedule of Activities [SoA]) and tumor imaging assessments until PD, start of another anticancer therapy, final cohort cut-off, whichever comes first, before moving to the Survival Phone Call Follow-Up Period.

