 2. Participants who discontinue study treatment **with PD** will be followed for safety in the Follow-Up Visit 1 occurring 3 months \pm 7 days from last IMP administration, before moving to the Survival Phone Call Follow-Up Period.

Participants who move into the **Survival Phone Call Follow-Up Period** will be contacted by telephone every 3 months \pm 14 days to assess for survival status. Updated survival status may be requested by the Sponsor at any time during the study. Survival Phone Call Follow-up will continue until death, participant request to discontinue from follow-up, or cut-off date for the given cohort final analysis has been reached, or upon cancellation of Survival follow-up in the given cohort at the discretion of the Sponsor at any prior timepoint whichever occurs first.

The cohort cut-off for the primary ORR endpoint analysis for each individual cohort is estimated to be approximately 9 months from the date of the last participant first infusion. This would allow the possibility to observe the response of the last participant for 6 months, assuming there is a response at first treatment assessment.

After the cohort cut-off date for the primary ORR analysis, participants can continue to receive IMP, if clinical benefit is observed, until full permanent discontinuation criteria described in **Section 7** are met and will continue to undergo all assessments as per the study schedule of activities.

For each cohort, the cut-off date for the final analysis (ie, analysis of secondary objectives and update of primary objective) will be 18 months from the corresponding cohort LPI. After this cut-off date for the final analysis, the participants of the given cohort still receiving study treatment in that specific cohort will be followed up as the cohorts after early termination described in **Section 10.1.9**.

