8.3.1 Time period and frequency for collecting AE and SAE information

All AEs, including adverse events of new onset, as well as worsening of baseline signs and symptoms will be collected throughout study period, from the signing of the informed consent form (ICF) until **30 days** following cessation of study treatment.

All SAEs and AESIs will be collected throughout the study period, from the signing of the informed consent form (ICF) until **90 days** following last administration of study treatment.

All SAEs and AESI will be recorded and reported to the Sponsor or designee immediately and under no circumstance should this exceed 24 hours, as indicated in Appendix 3 ([Section 10.3](#)). The Investigator will submit any updated SAE data to the Sponsor within 24 hours of it being available.

Investigators are not obligated to actively seek information on AEs or SAEs after conclusion of the study participation. However, if the Investigator learns of any SAE, including a death, at any time after a participant has been discharged from the study, and he/she considers the event to be reasonably related to the study intervention or study participation, the Investigator must promptly notify the Sponsor.

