8.3 ADVERSE EVENTS (AES), SERIOUS ADVERSE EVENTS (SAES) AND OTHER SAFETY REPORTING

Please refer to the master protocol.

8.3.1 Time period and frequency for collecting AE and SAE information.

Please refer to the master protocol for AEs and serious adverse events (SAEs) collection. For participants in Cohort A irAEs will be collected until 90 days following last administration of study treatment regardless of whether or not another anticancer therapy is initiated.

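### Follow-Up Visit 1 falls away for participants who stop without PD and then progress or start new therapy before month 3, although SAE, AESI and irAE collection runs to day 90; for those who stop with PD, SoA footnote d contradicts Section 4.1

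*Protocol*

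**What the plan says.** **Visit path, stopping without PD.** Master protocol Sections 1.1 and 4.1, item 1, schedule 3-monthly follow-up for safety together with "tumor imaging assessments until PD, start of another anticancer therapy, final cohort cut-off, whichever comes first, before moving to the Survival Phone Call" follow-up period. One set of stopping events governs both the safety visits and the imaging.

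**Visit path, stopping with PD.** Item 2 of the same sections says these participants "will be followed for safety in the Follow-Up Visit 1 occurring 3 months" after the last dose, before they move to the phone-call period. It contains no exit for new therapy.

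**SoA footnote d**, in Section 1.3 of both the master protocol and substudy 01, makes no such distinction: "Once the participant stops the tumor assessments due to PD or starts a new antineoplastic therapy, the participant moves into the Survival Follow-up Period". The calls that follow are for survival status. The SoA adds only the first subsequent anticancer therapy.

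**EOT visit.** The SoA times it at "30 days (+/- 7 days) after last IMP or at initiation of further therapy".

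**Collection duty.** Master protocol Section 8.3.1: "All SAEs and AESIs will be collected throughout the study period, from the signing of the informed consent form (ICF) until" 90 days after the last administration. All AEs are collected to 30 days. Neither rule has an exit for new therapy. Substudy 01 Section 8.3.1 adds for Cohort A that "irAEs will be collected until 90 days following last administration of study treatment regardless of whether or not another anticancer therapy is initiated".

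**The concern.** The collection rule and the visit rule do not match. The first continues to day 90 whatever treatment follows. The second can remove the visit at which day-90 information would be gathered.

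Follow-Up Visit 1 is also where the post-EOT laboratory work is set: hematology and chemistry (master Section 10.2, note a) and, in Cohort A, endocrine tests (substudy 01 Section 10.2). This matters because Section 8.3.2 prefers verbal questioning of the participant as the way to detect events, one AESI in Section 8.3.8 is a laboratory pattern, and substudy 01 Section 6.5.4.4 warns that immune-related events can appear months after the last pembrolizumab dose.

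Participants who stop without PD include those who stopped for toxicity, so the group exposed to the gap is not neutral with respect to safety. Safety is a secondary objective and the DMC reviews cumulative safety data.

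**Working it through.** **1. The plan's own safety figure.** No figure in the plan describes late follow-up. The nearest is in substudy 01 Section 9.2: the probability of seeing at least one event in 40 participants, 1 − (1 − p)^40. For p = 1%, 2% and 5% this gives 33.1%, 55.4% and 87.1%, as stated.

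**2. Rules side by side.**

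| Situation | Sections 1.1/4.1 | SoA footnote d | Section 8.3.1 |
|---|---|---|---|
| Stops without PD; PD or new therapy before month 3 | Safety visits end; phone calls | Phone calls | Collect to day 90 |
| Stops with PD, with or without new therapy | Follow-Up Visit 1, then phone calls | Phone calls | Collect to day 90 |

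In the first row the visit rules agree with each other and leave the duty in the last column without a scheduled contact. In the second row Section 4.1 serves the duty and footnote d, read as written, does not.

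**3. Is another AE contact scheduled?** In the master SoA the AE/SAE row has one mark after the treatment period, and its position lines up with Follow-Up Visit 1. The table layout is damaged in the copy at hand, so this rests on column position. It is consistent with the laboratory notes in Section 10.2. The survival calls carry no AE item.

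**4. Timing.** EOT is at 30 ± 7 days, so day 23 to 37. With 3 months taken as 91 days, Follow-Up Visit 1 falls at day 84 to 98.
- Last scheduled AE contact to the end of the 90-day window, without Follow-Up Visit 1: 90 − 37 = 53 to 90 − 23 = 67 days, and longer if EOT is brought forward.
- If new therapy starts on day 21 (an illustration), EOT is no later than day 21 and 30 − 21 = 9 days of the 30-day on-treatment period follow it. The ordinary EOT window already permits 30 − 23 = 7 days.

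**5. What a loss could mean.** Assume, since the documents give no share, that 10%, 25% or 50% of 40 participants had no late observation at all. For a late event with a true rate of 5%:

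| Share not observed | n observed | 1 − 0.95^n |
|---|---|---|
| 0% | 40 | 87.1% |
| 10% | 36 | 84.2% |
| 25% | 30 | 78.5% |
| 50% | 20 | 64.2% |

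These are worst cases, because Section 8.3.1 still requires the events to be collected.

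**The case against.** The best defence is that nothing in the protocol stops recording. Section 8.3.1 keeps the duty for every participant, substudy 01 makes it explicit for irAEs, and Section 7.1.1 keeps participants in the study for safety assessment. Footnote c, directly above footnote d, says that follow-up differs by reason for discontinuation and points to Section 4.1, so footnote d could be read as loose wording that Section 4.1 overrides.

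Much of this stands, and it rules out three stronger readings that a reader might infer:

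- *That any new therapy sends every participant straight to survival calls.* Section 4.1, item 2, keeps Follow-Up Visit 1 for those who stop with PD. For them the defect is a contradiction between two places, not a uniform skip.
- *That late toxicity is under-recorded and rates are biased downward.* Collection remains mandatory, so the documents support a risk and not a fact. Treatment-emergent events close at day 30, so losing a month-3 visit barely touches them.
- *That the days between contacts measure the loss, or that a stated number of participants is affected.* A fully compliant participant also has no scheduled visit between EOT and Follow-Up Visit 1. What is lost is one look-back visit with its laboratory tests. No share of participants can be derived from the documents.

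The defence does not close the gap for participants who stop without PD. Section 7.1.1 refers safety assessment back to the SoA, which is where the visit disappears. Section 8.3.3 concerns events already reported and, for those above Grade 1, itself allows follow-up to end at new therapy. A duty to collect new events with no named contact to serve it is more than an omitted detail when the stated visit rules remove the contact that existed.

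**Conclusion.** The point holds in limited form. For participants who stop without PD, PD or new therapy before month 3 removes the one post-EOT visit marked for AE/SAE assessment, while the 90-day duty for SAEs and AESIs (and for irAEs in Cohort A) continues. For participants who stop with PD, footnote d and Section 4.1 give sites opposite instructions.

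The consequence is a risk of under-ascertaining late events. Its size cannot be stated: it depends on how many participants stop without PD and then progress or start new therapy within 3 months, and on how well sites collect events without a visit. The detection figures above show only how far sensitivity could fall under assumed shares. Sample size and the ORR analysis are unaffected.

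The conclusion assumes that the AE/SAE mark belongs to Follow-Up Visit 1. The irAE rule is taken from substudy 01 and applies to Cohort A. The change is worth making, because the conflict is clear and the repair is small.

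**What to change.** - Reconcile footnote d (master protocol and substudy 01) and Sections 1.1/4.1, item 1, with Section 4.1, item 2, and Section 8.3.1. State that PD or the start of another therapy ends tumor imaging only.
- Keep a safety contact at 3 months for every participant before survival-only calls begin: Follow-Up Visit 1, or at least a phone contact at day 90 that asks about SAEs, AESIs and irAEs.
- Where EOT is brought forward to before day 30, add an AE phone contact at day 30 after the last dose.

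The cost is wording in the protocol and SoA plus a few extra contacts, since the visit already exists. A phone contact alone would not replace the laboratory tests. Some late events will be recorded while participants are on a subsequent therapy and will be harder to attribute.

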- o CT/MRI: The initial tumor imaging will be performed within 28 days prior to C1D1. Scans performed as part of routine clinical management are acceptable for use as the screening scan if they are of diagnostic quality and performed within 28 days prior to the date of enrollment. On study imaging will be performed every 9 weeks (63 ± 7 days) after the date of first IMP and if clinically indicated. Imaging studies should follow calendar days and should not be adjusted for delays in cycle starts or extension. The same imaging technique should be used in a participant throughout the trial. After week 45, tumor imaging should be performed every 12 weeks (84 ± 7 days). CT scan of the chest, abdomen, pelvis and any other locations with suspicion or evidence of disease involvement is required for the baseline assessment, during treatment period until PD. Per the primary tumor assessment criteria, after the first documentation of response or the first documentation of progression (if the participant is clinically stable), confirmatory imaging may be performed no fewer than 28 days later. Alternately, the scan performed at the next scheduled time point (eg, every 63 ± 7 days) may be used as confirmation. Tumor assessment is not needed for participants who start another anti-cancer therapy.

Abbreviations: ADA=anti-drug antibodies; AE=adverse event; AST=aspartate transaminase; ALT=alanine transaminase; C=Cycle; ANC=Absolute neutrophil count; AP=Alkaline phosphatase; BUN=Blood urea nitrogen; CRF=case report form; CRS=Cytokine release syndrome; CT=computed tomography; [REDACTED]; D=Day; ECG=electrocardiogram; ECOG=Eastern Cooperative Oncology Group; e-CRF=electronic case report form; EOT=end-of-treatment; FT4=free thyroxine; FU=follow-up; HBsAg=Hepatitis B surface antigen; HCV=Hepatitis C virus; ICF=Informed consent form; IMP=investigational med [REDACTED] ed ratio; LDH=Lactate hydrogenase; LVEF=left ventricular ejection fraction; MRI=magnetic resonance imaging; MUGA= multigated acquisition; PD=progressive disease [REDACTED] PDy=pharmacodynamic; PK=pharmacokinetic; PR=partial response; PS=Performance Status; SpO2= oxygen saturation; Q3W=every 3 weeks; RECIST=Response Evaluation Criteria in Solid Tumors; SAE=serious adverse event; T3=tri-iodothyronine; TSH=thyroid stimulating hormone; WBC=White blood cells.

